2.6 Correlative Studies Background

BH3 Profiling

This study will incorporate a laboratory technique known as BH3 profiling, which is a functional assay we previously developed that detects the proximity of malignant cells to the threshold of apoptosis (what we call 'priming') through physiologic interrogation of BCL-2 family members (Ryan, Brunelle, & Letai, 2010). To perform a BH3 profile, we add individual BH3-only peptides to gently permeabilized primary CLL cells and use fluorescence activated cell sorting (FACS) to determine the amount of mitochondrial depolarization induced by each peptide, as measured by cytochrome c release. We previously found that in a small, heterogeneously treated cohort of CLL patients, increased priming was associated with improved clinical response (M. S. [name] et al., 2012). Building on these initial studies, we will incorporate BH3 profiling into this clinical trial to determine whether priming predicts degree of clinical response in this larger, homogeneously treated patient population.

Genomic Markers

We will perform whole exome sequencing on CLL cells and normal tissue from patients at baseline to evaluate for somatic mutations that may confer drug sensitivity and resistance. Our group and others have recently identified recurrent somatic mutations in the CLL genome which appear to associate with prognosis; these include *NOTCH1* and *SF3B1* (Wang et al., 2011). At present, whether other recurrent mutations associate with prognosis is less clear. Our group has also recently found that the presence of subclonal driver mutations was associated in a retrospective analysis with time to next treatment (Landau et al., 2013). In this trial, we will assess all of these recently described mutations as well as the presence of a subclonal driver mutation as potential predictors of response and progression-free survival. We will also bank samples at time of relapse for repeat analysis by whole exome sequencing to assess for the acquisition of resistance mutations. We will also evaluate established CLL prognostic markers such as cytogenetics by FISH, *TP53* mutation, IGHV status, and ZAP-70 status, and will determine whether these factors are associated with response to AVO.

Single Cell Sequencing and Cell Free DNA Sequencing Studies

Next generation sequencing (NGS) techniques have the potential for revolutionizing the treatment of CLL by allowing the detection of minimal residual disease or resistance mutations at levels below the sensitivity of current assays. We plan on using single cell DNA sequencing and RNA sequencing to identify the presence of oncogenic mutations, resistance mutations, and transcriptomic profiles of circulating CLL cells at various time points during the course of therapy. We will also retain plasma samples collected at the same time for cell-free DNA analysis, making use of an orthogonal assay to verify or expand upon results obtained from single cell sequencing.

ClonoSEQ Next Generation Sequencing Studies

Although conventional minimal residual disease (MRD) testing in CLL provides reasonable sensitivity for residual disease detection, novel methods of MRD-detection may allow even more sensitive detection with the potential for better prognostic power. Adaptive, Inc. has an assay known as ClonoSEQ, in which a baseline sample of genomic DNA is extracted from tumor cells, amplified using locus-specific primer sets for *IGH* and *IGK* rearrangements, and sequenced. Once a patient achieves a MRD-negative state, a peripheral blood sample is examined to determine whether tumor DNA is still detectable. This will be one of the first novel-agent only based studies to utilize ClonoSEQ MRD testing in parallel with conventional MRD testing for CLL patients who achieve a CR.

3. PARTICIPANT SELECTION

3.1 Eligibility Criteria

Unless otherwise specified, laboratory tests required for eligibility must be completed within 2 weeks prior to start of protocol therapy. Baseline tumor measurements by CT or PET/CT scan must be performed within approximately 30 days of starting study treatment. Bone marrow biopsy within approximately 6 months prior to study treatment will be acceptable if there has not been significant anti-cancer therapy given since the test was performed.

Inclusion Criteria

Participants must meet the following criteria on screening examination to be eligible to participate in the study:

- Subjects must meet IWCLL 2018 guidelines for the diagnosis of CLL or SLL, or WHO 2017 guidelines for the diagnosis of B-prolymphocytic leukemia (B-PLL)
- In cohort 2, subjects must have *TP53*-aberrant disease defined as:
 - o Del(17p) detected by karyotype, FISH, or next-generation sequencing; OR
 - o TP53 mutation
- Participants must have measurable disease (lymphocytosis > 5,000 / μ l, or palpable or CT measurable lymphadenopathy \geq 1.5 cm, or bone marrow involvement \geq 30%).
- Subjects must not have received any prior systemic therapy for CLL or SLL due to
 previously meeting IWCLL 2018 guidelines and must currently have an indication for
 treatment as defined by the IWCLL 2018 guidelines, or must not have received therapy
 for B-PLL and must currently have an indication for treatment:
 - Massive or progressive or symptomatic splenomegaly; OR
 - o Massive lymph nodes, nodal clusters, or progressive lymphadenopathy; OR
 - Significant fatigue (i.e. ECOG PS 2 or worse; cannot work or unable to perform usual activities); OR
 - Fever ≥ 100.5 °F for 2 or more weeks without evidence of infection; OR
 - Night sweats for ≥ 1 months without evidence of infection; OR
 - Presence of weight loss $\geq 10\%$ over the preceding 6 months; OR
 - Progressive lymphocytosis with an increase of \geq 50% over a 2-month period or lymphocyte doubling time of less than 6 months; OR
 - Evidence of progressive marrow failure as manifested by the development of or worsening of anemia and/or thrombocytopenia.
 - Autoimmune anemia and/or thrombocytopenia that is poorly responsive to corticosteroids and another standard therapy such as rituximab
 - Symptomatic or functional extranodal involvement; OR
- Age greater than or equal to 18 years. Because CLL is extremely rare in persons <18 years of age, children are excluded from this study.

- ECOG performance status ≤2 (see Appendix A)
- Participants must have adequate organ and marrow function as defined below:
 - o total bilirubin ≤1.5 times upper limit of normal, unless there is disease involvement of the liver, hemolysis, or a known history of Gilbert's disease, in which case direct bilirubin must be ≤3 times the upper limit of normal
 - AST and ALT ≤ 2.5 times the upper limit of normal. If there is hemolysis or documented disease involvement of the liver, then patients with any AST or ALT abnormalities remain eligible.
 - o creatinine clearance (CrCl) ≥ 50 mL/min using 24-hour urine collection for creatinine clearance or calculated CrCl OR calculated glomerular filtration rate (GFR) ≥ 50 mL/min/1.73m² using the CKD-EPI equation
 - o PT/INR ≤2 times the upper limit of normal and PTT ≤2 times the upper limit of normal
 - o Absolute neutrophil count ≥750 cells/mm³ (0.75 x 109/L) or ≥500 cells/mm³ in subjects with documented bone marrow involvement
 - O Platelet count without transfusional support must be $\geq 50,000$ cells/mm³ or $\geq 30,000$ cells/mm³ in subjects with documented bone marrow involvement
- The effects of the study drugs on the developing human fetus are unknown. Women of child-bearing potential must agree to remain abstinent or use highly effective contraception (defined as contraceptive measures that result in a failure rate of <1% per year) during the treatment period and for at least 2 days after the last dose of acalabrutinib, 30 days after the last dose of venetoclax or 18 months after the last dose of obinutuzumab, whichever is longer. Men with female sexual partners of childbearing potential should agree to remain abstinent or use contraceptive measures which include a condom plus an additional contraceptive method that together result in a failure rate of<1% per year during the treatment period and for at least 30 days after the last dose of venetoclax or 6 months after the last dose of obinutuzumab, whichever is longer. Men should refrain from donating sperm during the same period. Should a woman become pregnant or suspect she is pregnant while she or her partner is participating in this study, she should inform her treating physician immediately.
- Ability to understand and the willingness to sign a written informed consent document.

Exclusion Criteria

Participants who exhibit any of the following conditions at screening will not be eligible for admission into the study:

- Participants who have a history of other malignancies except:
 - Malignancy treated with curative intent and with no known active disease present and felt to be at low risk for recurrence by treating physician. Current adjuvant hormonal therapy for disease treated with curative intent is permissible.
 - Adequately treated non-melanoma skin cancer or lentigo maligna without evidence of disease.

- o Adequately treated carcinoma in situ without evidence of disease.
- o Low-risk prostate cancer on active surveillance
- Participants who are receiving any other investigational agents.
- History of severe allergic reactions attributed to compounds of similar chemical or biologic composition to obinutuzumab, venetoclax, or acalabrutinib. Patients with reactions to other CD20 monoclonal antibodies (e.g. rituximab, ofatumumab) are not excluded.
- Unable to receive prophylactic treatment for pneumocystis, herpes simplex virus (HSV), and herpes zoster (VZV) at start of treatment
- Known or suspected Richter's transformation or known CNS involvement
- Concurrent systemic immunosuppressant therapy (e.g., cyclosporine A, tacrolimus, etc., within 28 days of the first dose of study drug or chronic administration of >20 mg/day of prednisone within 7 days of the first dose)
- Vaccinated with live, attenuated vaccines within 4 weeks of first dose of study drug.
- Ongoing or recent infection requiring intravenous antimicrobials at time of screening.
 Patients with ongoing use of prophylactic antibiotics are eligible as long as there is no
 evidence of active infection and the antibiotic is not included on the list of prohibited
 medications.
- Known bleeding disorders (e.g. von Willebrand's disease) or hemophilia.
- Presence of a gastrointestinal ulcer diagnosed by endoscopy within 3 months before screening.
- History of stroke or intracranial hemorrhage within 6 months prior to enrollment.
- Major surgery within 4 weeks of first dose of study drug. If a subject had major surgery
 greater than 4 weeks prior to the first dose, they must have recovered adequately from
 any toxicity and/or complications from the intervention before the first dose of study
 drug.
- Currently active, clinically significant cardiovascular disease, such as uncontrolled arrhythmia or Class 3 or 4 congestive heart failure as defined by the New York Heart Association Functional Classification; or a history of myocardial infarction, unstable angina, or acute coronary syndrome within 6 months prior to randomization. Patients with atrial fibrillation are allowed as long as they are adequately rate controlled.
- Baseline QTcF >480 ms. NOTE: This criterion does not apply to patients with a left bundle branch block.

• Patients who require warfarin or other vitamin K antagonists for anticoagulation (other anticoagulants are allowed).

- Patients who require treatment with proton pump inhibitors (see Appendix F). Subjects receiving proton pump inhibitors who switch to H2-receptor antagonists or antacids are eligible for enrollment on this study.
- Patients who require concurrent treatment with strong CYP3A inhibitors or strong CYP3A inducers are excluded from the study. If patients are receiving strong CYP3A inhibitors/inducers at time of screening but do not require continuous administration of these agents, these patients are eligible if there is a 3-day washout period between discontinuation of the strong CYP3A inhibitor/inducer and initiation of the first study drug, acalabrutinib.
- Patients who require concurrent treatment with P-gp inhibitors or narrow therapeutic
 index P-gp substrates are excluded from the study. If patients are receiving P-gp
 inhibitors or narrow therapeutic index P-gp substrates at time of screening but do not
 require continuous administration of these agents or can be switched to alternative agents,
 these patients are eligible if there is a 3-day washout period between discontinuation of
 the P-gp inhibitor and initiation of venetoclax.
- Unable to swallow tablets or malabsorption syndrome, disease significantly affecting gastrointestinal function, or resection of the stomach or small bowel if thought by the investigator to compromise systemic absorption, active, symptomatic inflammatory bowel disease or ulcerative colitis, or partial or complete bowel obstruction.
- Lactating or pregnant women are excluded from this study because venetoclax has been shown to decrease implantation, litter size, live fetuses, and fetal body weight in animal models. Because there is an unknown but potential risk for adverse events in nursing infants secondary to treatment of the mother with venetoclax, breastfeeding should be discontinued if the mother is treated with venetoclax. These potential risks may also apply to other agents used in this study.
- Patients with human immunodeficiency virus (HIV), human T cell leukemia virus (HTLV), active hepatitis C virus (HCV), or active hepatitis B virus (HBV) infection. HIV-positive participants are ineligible because of the potential for pharmacokinetic interactions between certain components of anti-retroviral therapy and venetoclax. Patients who are positive for hepatitis B core antibody or hepatitis B surface antigen must have a negative polymerase chain reaction (PCR) result before enrollment. Those who are PCR positive will be excluded. Those who are positive for either hepatitis B surface antigen and/or hepatitis B core antibody but negative for HBV DNA will be managed as detailed in section 5.4. Patients who are positive for HCV antibody must be negative for HCV by polymerase chain reaction (PCR) to be eligible for study participation.
- Unwilling or unable to participate in all required study evaluations and procedures.

• Unable to understand the purpose and risks of the study and to provide a signed and dated informed consent form (ICF) and authorization to use protected health information (in accordance with national and local subject privacy regulations)

- Significant co-morbid condition or disease which in the judgment of the Principal Investigator would place the patient at undue risk or interfere with the study
- Uncontrolled intercurrent illness including, but not limited to, ongoing or active infection, symptomatic congestive heart failure, unstable angina pectoris, cardiac arrhythmia, or psychiatric illness/social situations that would limit compliance with study requirements, compromise the subject's safety, or put the study outcomes at undue risk.

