contraception during the treatment period and for at least 2 days after the last dose of acalabrutinib, 30 days after the last dose of venetoclax, or 18 months after the last dose of obinutuzumab, whichever is longer. Men with female sexual partners of childbearing potential should agree to remain abstinent or use contraceptive measures which include a condom plus an additional contraceptive for at least 30 days after the last dose of venetoclax or 6 months after the last dose of obinutuzumab, whichever is longer.

• Ability to understand and the willingness to sign a written informed consent document.

Exclusion Criteria

- Participants who have a history of other malignancies, with certain exceptions including early stage malignancies treated with curative intent or low risk neoplasms managed with active surveillance
- Participants who are receiving any other investigational agents
- History of severe allergic reactions attributed to compounds of similar chemical or biologic composition to obinutuzumab, venetoclax, or acalabrutinib. Patients with reactions to other CD20 monoclonal antibodies (e.g. rituximab, ofatumumab) are not excluded.
- Unable to receive prophylactic treatment for pneumocystis, herpes simplex virus (HSV), and herpes zoster (VZV) at start of treatment
- Known or suspected Richter's transformation or known CNS involvement
- Concurrent systemic immunosuppressant therapy (e.g., cyclosporine A, tacrolimus, etc., within 28 days of the first dose of study drug or chronic administration of >20 mg/day of prednisone within 7 days of the first dose)
- Vaccinated with live, attenuated vaccines within 4 weeks of first dose of study drug.
- Ongoing or recent infection requiring intravenous antimicrobials at time of screening
- Known bleeding disorders (e.g. von Willebrand's disease) or hemophilia.
- Presence of a gastrointestinal ulcer diagnosed by endoscopy within 3 months before screening.
- History of stroke or intracranial hemorrhage within 6 months prior to enrollment.
- Major surgery within 4 weeks of first dose of study drug. If a subject had major surgery
 greater than 4 weeks prior, they must have recovered adequately from any toxicity and/or
 complications from the intervention before the first dose of study drug.

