7.3.1.1 Pregnancies

Pregnancies in Female Patients

If a female patient becomes pregnant while receiving the study drugs or within 18 months after the last dose of obinutuzumab or 30 days after the last dose of venetoclax or acalabrutinib, whichever is longer, a report should be completed and expeditiously submitted to AstraZeneca and Genentech. Follow-up to obtain the outcome of the pregnancy should also occur.

Pregnancies in Female Partners of Male Patients

If the female partner of male patients become pregnant while receiving the study drug or within 3 months after the last dose of obinutuzumab or 30 days after the last dose of venetoclax or acalabrutinib, whichever is longer, a report should be completed and expeditiously submitted to Genentech and AstraZeneca.

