While such reports are not serious adverse events per se, as defined herein, any reports of pregnancy (including pregnancy occurring in the partner of a male study subject), where the fetus may have been exposed to any of the study drugs, shall be transmitted to Genentech and/or AstraZeneca (depending on which drugs the subject was exposed to) within fifteen (15) calendar days of the awareness date. Pregnancies will be followed up until the outcome of the pregnancy is known, whenever possible, based upon due diligence taken to obtain the follow-up information.

Pregnancies in Female Partners of Male Patients

Male patients will be instructed through the Informed Consent Form to immediately inform the investigator if their partner becomes pregnant during the study or within 3 months after the last dose of obinutuzumab or 30 days after the last dose of venetoclax . A Clinical Trial Pregnancy Reporting Form should be completed and submitted to Genentech within thirty (30) calendar days of the awareness date.

Adverse Events of Special Interest

AESIs shall be forwarded to Genentech and AstraZeneca within fifteen (15) calendar days of the awareness date.

Special Situation Reports

In addition to all adverse events, pregnancy reports and AESIs, the following other Special Situations Reports (even in the absence of an Adverse Event) should be collected and transmitted to (depending on which drugs the subject was exposed to) Genentech within thirty (30) calendar days and AstraZeneca within fifteen (15) calendar days:

- Data related to study drug usage during breastfeeding.
- Data related to **overdose**, **abuse**, **misuse or medication error** (including potentially exposed or intercepted medication errors). Medication errors refers to any error in the prescribing, dispensing, or administration of a medicinal product while in the control of the healthcare professional, patient or consumer.
- Occupational exposure refers to the exposure to a medicinal product as a result of one's professional or nonprofessional occupation.
- Data related to suspected transmission of an infectious agent via a medicinal product
- Suspected Adverse Reaction related to quality defect or falsified medicinal products (whether suspected or confirmed)

In addition, reasonable attempts should made to obtain and submit the age or age group of the patient, in order to be able to identify potential safety signals specific to a particular population.

Product Complaints and Reporting

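### Partner-pregnancy reporting stops 3 months after obinutuzumab while male contraception runs 6 months, leaving a gap for men who stop both oral drugs early; the 15- and 30-day limits to Genentech are not related to each other

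*Combined protocol and SAP*

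**What the plan says.** **Contraception.** The synopsis (Key Eligibility Criteria) asks men with partners of childbearing potential to use contraception for at least "30 days after the last dose of venetoclax or 6 months after the last dose of obinutuzumab, whichever is longer". Section 3.1 sets the same period and applies it to sperm donation: "or 6 months after the last dose of obinutuzumab, whichever is longer. Men should refrain from donating sperm during the same period". Section 3.1 also says that a woman who becomes pregnant "while she or her partner is participating in this study, she should inform her treating physician immediately".

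**Reporting window.** Section 7.3.1.1 makes a partner pregnancy reportable if she should "become pregnant while receiving the study drug or within 3 months after the last dose of obinutuzumab", or within 30 days after venetoclax or acalabrutinib, taking the longer. For female patients the same section uses "within 18 months after the last dose of obinutuzumab or 30 days after the last dose of venetoclax or acalabrutinib, whichever is longer".

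**Instruction to men.** Under section 7.4 (Pregnancies in Female Partners of Male Patients), the consent form will carry this instruction for men: "immediately inform the investigator if their partner becomes pregnant during the study or within 3 months after the last dose of obinutuzumab". The only other period given there is 30 days from the end of venetoclax. Acalabrutinib and the longer-of rule do not appear.

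**Deadlines.** Section 7.4 (Pregnancy Reports) gives 15 calendar days from awareness for "any reports of pregnancy (including pregnancy occurring in the partner of a male study subject". The partner-pregnancy paragraph that follows says: "A Clinical Trial Pregnancy Reporting Form should be completed and submitted to Genentech within thirty (30) calendar days". Section 7.3.1.2 puts pregnancies on the serious-adverse-event timeline, and section 7.4 (Serious Adverse Drug Reactions) sets that at 15 calendar days to Genentech.

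**The concern.** A reporting window is meant to catch pregnancies conceived while the protocol still regards exposure as a risk. Here the protocol treats the second three months after obinutuzumab as risky enough to require contraception and bar sperm donation, yet leaves them outside the partner-pregnancy window for some men. No reason is given for this one shorter period. A contraceptive failure in that interval could go unrecorded.

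The deadline wording raises a different problem, which could arise with any partner pregnancy. Whoever submits the report could rely on the 30-day sentence under the partner-pregnancy heading and pass the 15-day limit in the paragraph above it.

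**Working it through.** The plan gives no figure to reproduce; the check compares texts and then works out the reach of the mismatch.

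**1. Reporting against contraception, by drug** (sections 3.1 and 7.3.1.1)

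| Who, drug | Reporting | Contraception | Difference |
|---|---|---|---|
| Women, obinutuzumab | 18 months | 18 months | 0 |
| Women, venetoclax | 30 days | 30 days | 0 |
| Women, acalabrutinib | 30 days | 2 days | +28 days |
| Men, venetoclax | 30 days | 30 days | 0 |
| Men, acalabrutinib | 30 days | none set | reporting longer |
| Men, obinutuzumab | 3 months | 6 months | **−3 months** |

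Three of the six rows differ, but only the last has reporting shorter than contraception.

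**2. Reach of the gap under section 7.3.1.1**

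Inputs: one month = 365.25/12 = 30.44 days, so 3 months = 91.3 days and 6 months = 182.6 days. Cycles last 28 days (section 5.1). The last planned obinutuzumab dose is on cycle 7 day 1, which is study day 6 × 28 + 1 = 169. Let *t* be the days from the last obinutuzumab dose to the last dose of whichever oral drug stops later.

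Gap = max(0, 182.6 − max(91.3, *t* + 30)).

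- The gap is zero once *t* + 30 ≥ 182.6, that is *t* ≥ 152.6 days (study day 169 + 152.6 ≈ 322, in cycle 12).
- The gap is at its maximum, 182.6 − 91.3 = 91.3 days, while *t* + 30 ≤ 91.3, that is *t* ≤ 61.3 days (study day 169 + 61.3 ≈ 230).

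| Both oral drugs stopped at end of | *t* (days) | Gap (days) |
|---|---|---|
| Cycle 7 | 27 | 91.3 |
| Cycle 8 | 55 | 91.3 |
| Cycle 9 | 83 | 69.6 |
| Cycle 10 | 111 | 41.6 |
| Cycle 11 | 139 | 13.6 |
| Cycle 12 | 167 | 0 |
| Cycle 15 | 251 | 0 |

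For the largest gap, the 3-month period ends at about study day 169 + 91.3 = 260 and the contraception period at about 169 + 182.6 = 352.

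**3. Section 7.4 against 7.3.1.1**

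The two describe different windows. If a man stops venetoclax and continues acalabrutinib alone, section 7.3.1.1 runs to 30 days after acalabrutinib if that is later. The instruction in section 7.4 reaches that far only through its reference to pregnancies during the study.

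**4. Deadlines**

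The event, the recipient and the starting point (awareness date) are the same, with limits of 15 and 30 calendar days: a difference of 30 − 15 = 15 days. Section 7.3.1.2 combined with the serious-event deadline in section 7.4 points to 15 days for the report.

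**The case against.** **The window.** Nothing in the protocol requires the reporting and contraception periods to match, and other rows of the table differ too. Every planned course continues both oral drugs through at least cycle 15, where the gap is zero. Other text also limits the harm. Section 3.1 asks a partner to tell her physician while the man is participating. The instruction in section 7.4 covers pregnancies during the study. A man taken off treatment normally stays in follow-up under section 5.6. Sections 7.3.1.2 and 7.4 put no end date on reporting a pregnancy once it is known. Section 7.3.1.3 asks, after the reporting period, for serious events believed related to study drug, including congenital anomalies. All of this stands and makes the point small. It does not explain why the one shorter period is the one where the protocol requires six months of contraception.

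**The deadlines.** A reader might infer that the two sentences contradict each other. The documents do not establish that. The opening text of section 7.4 sends pregnancy reports to Genentech, including partner pregnancies, on a MedWatch or CIOMS I form, whereas the 30-day sentence names a separate pregnancy form. A report by day 15 and a form by day 30 would satisfy both. That sequence is nowhere stated, however, so the ambiguity remains.

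**Conclusion.** The point holds as a minor safety-reporting inconsistency. Up to about 91 days of the required contraception period lie outside the section 7.3.1.1 window, and only for men who stop both oral drugs less than about 153 days after their last obinutuzumab dose. The cycle-by-cycle figures assume the last obinutuzumab dose on cycle 7 day 1, no delays, and average-length months; the 153-day threshold applies whenever that last dose falls.

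Two wider readings are tempting. One is that every man has a three-month blind spot; the longer-of rule in section 7.3.1.1 excludes that. The other is that an affected man and his partner receive no instruction to report. This cannot be shown: follow-up and the partner sentence in section 3.1 cover men still on study, and the consent form that carries the instruction is not in the review copy.

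The number of affected men is unknown. Section 13.2 plans 50 men among 71 participants. Section 2.4 reports no discontinuation for toxicity among the first 25 enrolled, of whom only 12 had reached triple therapy, so a small group is likely but not assured.

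On deadlines, the finding is an unexplained 15-day difference. If the 30-day sentence were applied to the initial report, that report could be up to 15 days late. Nothing here affects endpoints, dosing or analysis.

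**What to change.** 1. In section 7.3.1.1 and in the partner-pregnancy paragraph of section 7.4, change 3 months to 6 months after the last obinutuzumab dose.
2. In that paragraph of section 7.4, add acalabrutinib to the 30-day period and state that the longer period applies, so that it matches section 7.3.1.1.
3. In the same paragraph, state that the initial partner-pregnancy report is due to Genentech within 15 calendar days of awareness. Keep day 30 for the completed form only if two steps are intended; otherwise set 15 days for both.
4. Check whether the consent form repeats the 3-month figure, and change it if so.

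The cost is a few wording edits in a routine amendment, with IRB approval at participating sites (Appendix J), and slightly longer pregnancy notification for a few men.
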